2. SCHEDULE OF ACTIVITIES (SOA)

If assessments are scheduled for the same nominal time, THEN the assessments should occur in the following order pre-dose:

- 1. Telemetry start
- 2. spirometry
- 3. 12-lead electrocardiogram (ECG)
- 4. vital signs
- 5. blood draws

and in the following order post-dose:

- 1. 12-lead ECG
- 2. vital signs
- 3. blood draws
- 4. spirometry

Note: The timing of the assessments should allow the blood draw to occur at the exact nominal time.

• The timing and number of planned study assessments, including safety, pharmacokinetic, or others assessments may be altered during the course of the study based on newly available data (e.g., to obtain data closer to the time of peak plasma concentrations) to ensure appropriate monitoring.

- Any change in timing or addition of time points for any planned study
 assessments must be documented in a Note to File which is approved by the
 relevant GlaxoSmithKline (GSK) study team member and then archived in the
 study sponsor and site study files, but this will not constitute a protocol
 amendment.
- The institutional review board (IRB)/independent ethics committee (IEC) will be informed of any safety issues that require alteration of the safety monitoring scheme or amendment of the Informed Consent Form.

Screening and follow-up procedures for all cohorts

Procedure	Screening, \leq 30 days before D1 for Part 1 or \leq 45 days before D1 for Part 2^1	Follow up 30±2 days after the last dosing day ²	Notes
Informed consent	Х		Screening assessments can be performed over multiple screening visits
Inclusion and exclusion criteria	Χ		2. All male participants will be called approximately 7 months after the follow-up visit to
Demography	X		ensure no partner pregnancy
Full physical examination including height and weight, oral examination	Х		 If test otherwise performed within 3 months prior to first dose of study treatment, testing at screening is not required
Brief physical examination, oral examination		Х	 To be drawn fasting (for at least 8 h) To be administered to participants with COPD only, 15-30 minutes prior to spirometry
Medical history (includes substance usage and Family history of premature CV disease)	Х		 To be done at screening for participants with COPD only, following salbutamol dosing To be performed in the bronchoalveolar lavage (BAL) cohorts only to confirm participant eligibility

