Repeat dose schedule to be followed for repeat dose cohorts in Parts 1 and 2 (other than Cohort A Part 1)

Procedure	Treatment Period, Days															
	-1	1	2	3	4	5	6	7	8	9	10	11	12	13	14	15
Inclusion and exclusion criteria	Х															
Brief physical examination, oral examination	Х															Χ
Substance testing (drugs, alcohol, tobacco1)	Х															
Inhaler device training ²	Х															
Serum pregnancy test in women	Х															
Admittance to clinic	Х															
Randomization	X3															
Discharge																X ⁴
Dosing procedure training with bystanders		X 5														
Haematology, clinical chem and urinalysis (include liver chem) ⁶	Х							Χ								Χ
Spirometry		X ⁷		X8			X8					X8			X ⁷	
Telemetry (starting 30 min pre-morning dose and continuous at least 4h post-morning dose)		Х						Х						X9		
12-lead ECG and vital signs ¹⁰	XXX	Χ		Х	Χ		Х	Χ	Х		X11		X11			
CCI15106-IP or placebo treatment BID, device incident assessment BID ¹²		Х	Х	Х	Х	Х	Х	Х	Х	Х	Х	Х	Х	Х	Х	
PK blood sample ¹³		Χ	Χ		Χ		Χ		Χ		Χ		Χ		Χ	Χ
BAL	X14															
Urea blood sample	X15															
AE review	←========→															
SAE review	←======== →					\rightarrow										
Concomitant medication review	←						\rightarrow									

- 1. Tobacco test to be performed only in healthy participants
- 2. Day -1 inhaler training may be done on Day 1 instead, before the first dose administration. Other time-points may be added per investigators discretion.
- 3. Can be performed on Day 1 prior to dosing
- 4. After all procedures and assessments are complete
- 5. To be done only in Cohort(s) where bystanders are present. Can be performed on Day -1 instead, if desired. Other time-points may be added per investigators discretion.
- 6. To be drawn fasting (for at least 8 h)
- 7. To be performed at the following timepoints in the mornings only: pre-dose, and 0.25 (in participants with COPD only), 0.5, 1, 4 h post-dose
- 8. To be performed at the following timepoints in the mornings only: pre-dose and 4 h post-dose

2016N290366_02 **CONFIDENTIAL** 205822

- 9. Telemetry may be performed on Days 11 or 12 instead, not to coincide with the BAL procedure.
- 10. ECG and vital signs to be obtained 2 h after the morning dose
- 11. When BAL is performed, vital signs and ECG will be performed before and after the procedure and oxygen saturation will be measured continuously.
- 12. For cohort with bystanders, BID doses may have ± 1.5 h window.

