	 Bronchospasm has been reported following CCI15106/ribavirin use by patients with COPD and asthma. 	
	Pulmonary adverse reactions reported in clinical studies or in postmarketing use of aerosolized CCI15106/ribavirin include bacterial pneumonia, pneumothorax, laryngitis, pharyngitis, dyspnoea, cough, hypo- and hyperventilation, apnoea, and bronchospasm.	
Haemolytic anaemia	The primary toxicity of approved formulations of CCI15106 is haemolytic anemia, which was observed in 10% of oral CCI15106 plus interferon alpha2b combination-treated participants and occurs within 1 to 2 weeks of start of therapy [Rebetol USPI, 2015]. Haemolytic anemia associated with CCI15106 may result in worsening of cardiac disease that has led to fatal and nonfatal myocardial infarction. CCI15106 is known to accumulate in the red blood cells and may cause hemolysis, which may result in increased uric acid [De Franceschi, 2000]. Anemia has been shown to occur frequently with experimental oral and intravenous CCI15106 in humans [Virazole USPI, 2013]. Haemolytic anaemia is monitorable and reversible with reduction / cessation of treatment [Rebetol USPI, 2015].	Participants will be monitored regularly with complete blood counts and hematocrit, as per SoA (Section 2). Participants with hemoglobinopathies will be excluded. Due to the short dose and duration and the red blood cell count monitoring in place, laboratory monitoring for hemolysis is not warranted in this study. Participants will have an ECG assessment prior to and during the study. Cardiac monitoring, including assessment of blood pressure and heart rate, along with 12-lead electrocardiograms (ECGs) will be performed, per protocol. If cardiac status deteriorates on therapy, study medication
	GSK formulations:	should be suspended and/or discontinued.
	In toxicity studies conducted by GSK, mild anaemia was seen in 4 week studies following inhalation administration of CCI15106:trehalose:trileucine particles (rat and dog) or CCI15106-IP (rat only).	

Potential Risk of Clinical Significance	Summary of Data/Rationale for Risk	Mitigation Strategy

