For Cohort A Part 1, 60 mg single dose will be administered on Day 1; 120 mg single dose will be administered on Day 3; and then 30 mg dose will be administered BID on Days 6-19. Participants will report to the unit on Day -1 for assessments and randomization (randomization can also be done on Day 1, prior to dosing). Participants will be dosed the following morning on Day 1 followed by post-dose assessments. Blood for PK assessments will be collected for the next 48 hours (h). On Day 3 (after collection of 48 h PK time point), participants will receive a single dose of 120 mg followed by post-dose assessments and PK assessments for the next 72 h. Repeat dosing will begin on the morning of Day 6 (after collection of 72 h PK time point) and will continue for 14 days BID. Participants will remain in the unit for additional 2 days until 72 h PK timepoint is collected. Dosing frequency and duration may be adjusted based on emerging safety and tolerability data. Participants will return for the follow-up visit approximately 30 days after discharge. All male participants will also be called approximately 7 months after the follow-up visit to ensure no partner pregnancy.

For Cohort B Part 1, Repeat Dose SoA will be followed for the duration of the study. Participants will report to the unit on Day -1 for assessments and randomization (randomization can also be done on Day 1, prior to dosing). Dosing will begin on the morning of Day 1 and continue for 14 days BID. Dosing frequency and duration may be adjusted based on emerging safety and tolerability data. BAL procedure will be performed as soon as possible (within 1 h) after the first (morning) dose on one of the following days: 10, 11, 12, or 13. Participants will be discharged on Day 15 following completion of all post-dose assessments after the last dose, or later if additional PK collection or other assessments are required. Participants will return for the follow-up visit approximately 30 days after discharge. All male participants will also be called approximately 7 months after the follow-up visit to ensure no partner pregnancy.

For Cohort C Part 1, 14 healthy participants will be enrolled to evaluate bystander exposure and will follow Cohort C Part 1 SoA. Bystanders and air exposure will be evaluated concomitantly with Cohort B Part 1. Bystanders will report to the unit on Day

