8.1.3. Other Stopping Criteria

Dosing will be stopped for any individual participant in case of SAEs and in case of any AEs which in the opinion of the investigator might jeopardise the health of the trial participant.

Additionally, dosing will be stopped and the study will be put on halt if any of the below scenarios occurred. If following an internal safety review the Sponsor deems it appropriate to restart the trial, this can be done following approval of a substantial amendment:

Two (2) or more subjects, within a dose-level, receiving study treatment experience grade 3 respiratory adverse event that are deemed possibly or probably related to study drug by the investigator.

Two (2) or more subjects, within a dose-level, receiving study treatment experience a grade 3 hematologic adverse event that are deemed possibly or probably related to study drug by the investigator.

Two (2) or more subjects, within a dose-level, receiving study treatment experience severe hypersensitivity related adverse event that are deemed possibly or probably related to study drug by the investigator.

Two (2) or more subjects, within a dose-level, receiving study treatment experience a grade 3 vital signs (heart rate and/ or blood pressure) adverse event that are deemed possibly or probably related to study drug by the investigator.

One (1) or more subjects receiving study treatment experience anaphylaxis that is deemed possibly or probably related to study drug by the investigator.

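### Cohorts B schedule no blood count on Days 8-14 of dosing; a haematology tube at the existing Day 10 pre-dose draw would be a cheap, modest safety gain

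*Protocol*

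**What the plan says.** Protocol Section 2, repeat-dose schedule (both Cohorts B): the row "Haematology, clinical chem and urinalysis (include liver chem" is marked on Days -1, 7 and 15. Dosing is twice daily on Days 1-14. Section 5.1 confirms that Day 15 comes after dosing: "Participants will be discharged on Day 15 following completion of all post-dose assessments after the last dose".

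Section 3.3.1 states the hazard in these terms: "The primary toxicity of approved formulations of CCI15106 is haemolytic anemia". For its frequency and timing, the same row of the risk table gives a figure from combination therapy: "which was observed in 10% of oral CCI15106 plus interferon alpha2b combination-treated participants and occurs within 1 to 2 weeks of start of therapy". It adds: "Haemolytic anaemia is monitorable and reversible with reduction / cessation of treatment". The mitigation column reads: "Participants will be monitored regularly with complete blood counts and hematocrit, as per SoA (Section 2". That column also rules out laboratory monitoring for haemolysis, partly because red cell counts are being monitored.

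Section 8.1.3 halts the study on, among other triggers, "Two (2) or more subjects, within a dose-level, receiving study treatment experience a grade 3 hematologic adverse event" judged related to study drug. It also stops dosing in any one participant with an SAE, or with an AE that the investigator thinks might endanger health.

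Testing can be extended. Section 2 says that planned assessments "may be altered during the course of the study based on newly available data", and Appendix 2 lets the investigator order extra tests at any time. Section 9.4.7 has clinically significant abnormal results repeated. None of these schedules a count in the second week.

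**The concern.** The onset window that Section 3.3.1 cites covers both weeks of the dosing period, but the only scheduled count that can change dosing is at the end of the first week. A haemoglobin fall starting after Day 7 meets no scheduled test until dosing is over. Stopping early would depend on symptoms, vital signs, ECG or a test ordered at discretion, and the haematologic halting rule receives no scheduled result on Days 8-14.

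This matters most in Cohort B Part 1, the first repeat dosing at 60 mg twice daily. It also affects interpretation. Every Cohort B participant has bronchoalveolar lavage (BAL) on one of Days 10-13, and Section 3.3.1 lists bleeding among the complications of bronchoscopy. The only scheduled count after Day 7 therefore follows BAL, so a low Day 15 haemoglobin cannot be cleanly separated from procedural blood loss.

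**Working it through.** **Inputs.** Haematology, PK and dosing days: Section 2, repeat-dose schedule and footnotes 13-14, and the Cohort A Part 1 schedule. Doses and BAL days: Section 5.1. Exposure: Section 5.5, Table 1. Time windows and the blood cap: Section 9. The schedule has no Day 0.

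**1. The plan's own figure.** Table 1 gives AUC(0-24) of 6,150 ng.h/mL at 60 mg twice daily and 50.722 µg.h/mL for oral ribavirin. 50,722 / 6,150 = 8.2, matching the printed margin of 8. Against 30 mg twice daily: 6,150 / 3,080 = 2.0.

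**2. Dosing after the Day 7 count.** Total: 14 × 2 = 28 doses, 28 × 60 = 1,680 mg. The draw time on Day 7 is not stated. If drawn before the morning dose, 8 × 2 = 16 doses (960 mg) follow; if after both Day 7 doses, 7 × 2 = 14 doses (840 mg).

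**3. Gaps between counts.** Day -1 to Day 7 is 7 days; Day 7 to Day 15 is 15 − 7 = 8. Adding one count at an existing second-week pre-dose PK draw gives:

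| Added day | Gaps (days) | Longest overall | Longest after Day 7 |
|---|---|---|---|
| none | 7, 8 | 8 | 8 |
| 8 | 7, 1, 7 | 7 | 7 |
| 10 | 7, 3, 5 | 7 | 5 |
| 12 | 7, 5, 3 | 7 | 5 |
| 14 | 7, 7, 1 | 7 | 7 |

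Counted from the first dose instead of Day -1, Day 10 lowers the longest interval from 8 to 6 days. Over the whole schedule every option gives 7, so the longest gap does not choose the day.

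**4. Doses that could still be spared,** if the result is acted on from the next morning. Day 10: Days 11-14 = 4 × 2 = 8 doses (480 mg). Day 12: Days 13-14 = 2 × 2 = 4 doses (240 mg). Day 8 leaves more (Days 9-14 = 6 × 2 = 12) but comes only one day after the Day 7 count.

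**5. Last count before BAL.** Now: 10 − 7 = 3 to 13 − 7 = 6 days old. With Day 10, for BAL on Days 11-13: 1 to 3 days old. For BAL on Day 10, the pre-dose window opens 60 min before dosing and BAL follows within 1 h after it, so at most about 2 h separate draw and procedure. The result would probably not be back, and the usable count would still be Day 7.

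**6. Cohort A Part 1.** Counts after baseline fall on Days 2, 5, 12 and 22; repeat dosing at 30 mg twice daily runs on Days 6-19. Day 12 is repeat-dosing day 12 − 6 + 1 = 7, and Day 22 is 22 − 19 = 3 days after the last dose. Total dose is 60 + 120 + 28 × 30 = 1,020 mg, or 1,020 / 1,680 = 61% of the Cohort B total. No dosed cohort has a scheduled count in its second week of repeat dosing.

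**The case against.** The strongest reply is that the monitoring level was weighed. Section 3.3.1 judges haemolysis tests unnecessary given the dose, duration and red cell counts. Days 7 and 15 bracket the cited window, and that window comes from oral drug plus interferon at much higher exposure. Existing cover is real: the Day 7 panel includes reticulocytes and bilirubin; low haemoglobin and known haemoglobinopathy are excluded; participants stay in the unit, with ECG and vital signs on Days 8, 10 and 12; extra tests are allowed. Cohort B Part 1 follows review of Cohort A, and Cohort B Part 2 follows review of all Part 1 data, which includes Day 15 counts at the same planned dose. All of this stands and keeps the point modest. None of it puts a scheduled count in the second week.

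A second reply is that the fix secures little. Section 8.1.3 sets no individual haemoglobin threshold, and the grading guidance printed in Appendix 4 covers vital signs and allergic reactions, not haematology. That also stands: a reader might infer that 8 doses would be saved, but 8 is an upper bound. It needs a fall already visible on Day 10, a result by the Day 11 morning and the investigator's decision to stop. Nor should a reader infer that every BAL would be preceded by a fresh, usable count, as step 5 of the working shows.

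**Conclusion.** The point holds as a cheap safety improvement of modest size. In each Cohort B, 14 participants (12 active) take 14 or 16 of their 28 doses after the only scheduled on-treatment count, and Cohort A Part 1 does not cover the second week either.

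Two stronger readings are not supported. A reader might infer that the schedule contradicts Section 3.3.1. It does not: that section promises regular counts as per the schedule, and the schedule has them. A reader might also infer that one extra count brings the longest gap down to 5 days. It does not: the 5 days apply only after Day 7, and the unchanged 7 days from Day -1 to Day 7 become the longest gap.

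The case for Day 10 rests on the doses still to come (8 against 4 for Day 12) and on its place before every BAL, so that a low value cannot be due to procedural bleeding. How likely a second-week fall is at this exposure cannot be worked out from the protocol.

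**What to change.** In the repeat-dose schedule for Cohorts B, add a haematology-only panel (haemoglobin, haematocrit, RBC count, reticulocytes) on Day 10, drawn with the existing pre-dose PK sample. Participants are already fasting then (Section 6.3.1). Ask the local laboratory for the result before the Day 11 morning dose, and handle it under Sections 8.1.3 and 9.4.7 as they stand.

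Cost: one mark in the schedule, one extra tube and the local laboratory charge for each of 28 participants; no new visit, staff or procedure. Tube volumes are not given, so the blood total rests on assumptions. PK and urea blood is (2 × 11 + 7 + 1 + 1) × 3 + 2 = 95 mL. Assuming 10-20 mL for each of the five scheduled panels and 3-5 mL for the new tube, the total is 95 + 5 × 10 + 3 = 148 mL to 95 + 5 × 20 + 5 = 200 mL, excluding other screening tests, against the 500 mL cap.

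What remains: Days 11-14 still have no scheduled count.

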3. INTRODUCTION

3.1. Study Rationale

This study is the first administration of CCI15106-IP (CCI15106:polyvinyl alcohol 99:1 w/w 0.9x1 µm cylinder shape crystalline particles produced using Liquidia's Particle Replication In Non-wetting Templates [PRINT] technology) to humans. The study will evaluate the safety, tolerability, and lung and systemic pharmacokinetics (PK) of single and repeat ascending doses of CCI15106-IP delivered by inhalation in healthy participants and in participants with moderate chronic obstructive pulmonary disease (COPD). The study will use a Monodose RS01 device for drug delivery by inhalation.

A different formulation of CCI15106 (CCI15106:Trehalose:Trileucine 35/55/10 w/w 1 μ m pollen shape particles) has been previously administered to humans in the first time in human study (FTiH) 202031. That formulation was referred to as CCI15106 capsules for inhalation (CCI15106-CFI).

The intention of this study is to provide sufficient information regarding the safety of the molecule to inform progression to further repeat dose and proof of concept studies. The dose range proposed in this study is based on a starting dose previously investigated with the different formulation in the FTiH and escalating to a dose not to exceed the no observed adverse effect level (NOAEL) in the most sensitive species (Section 5.5).

The other intention of this study is to investigate the level of CCI15106 that will be released into the air and may be found in the blood of the bystanders around participants inhaling CCI15106-IP.

3.2. Background

CCI15106 is ribavirin, which is a generic, broad spectrum nucleoside antiviral, discovered in the early 1970s, with both clinical and nonclinical data available, which is approved and used for oral administration in the treatment of chronic hepatitis C virus. It is also approved for respiratory syncytial virus (RSV) bronchiolitis by pulmonary inhalation in paediatric patients. CCI15106 is active versus RSV, human metapneumovirus, parainfluenza, influenza, adenovirus, and human rhinovirus (HRV), although HRV is 4-15-fold less susceptible than the others (GlaxoSmithKline Document Number 2015N249287_00). Based upon published data coronaviruses could also be susceptible without co-administration of interferon [Kurai, 2013, Morgenstern, 2005]. CCI15106 is not considered to be the active form, rather it is actively transported into target organs/cells and converted to ribavirin triphosphate (RTP) believed to be the active form against the viruses [Thomas, 2012]. The major limitation of the use of CCI15106 is hemolytic anemia due to accumulation of RTP in red blood cells and teratogenicity.

Liquidia's Particle Replication In Non-wetting Templates (PRINT) technology uses lithographic etching processes to produce particles with highly defined size and shape. CCI15106 plus the excipient, polyvinyl alcohol, are combined in a ratio of 99:1 w:w using Liquidia's technology to produce CCI15106-IP, a highly dispersible powder of uniform 0.9x1 µm cylinder shape particles which has afforded a 24-fold increase in lung

concentration at maximum (Cmax) relative to micronised CCI15106:Lactose formulation in a solid dose inhaled rat PK study (GlaxoSmithKline Document Number 2015N242219_00 [N20691-39]). The size and uniformity of the Liquidia particles provides an opportunity to improve the efficiency of CCI15106 administration to the lung while limiting systemic exposure that has the potential to limit hemolytic anemia and teratogenicity.

205822

Acute exacerbations of COPD are a significant cause of morbidity and mortality [Vestbo, 2013; Kurai, 2013]. Multiple studies show that viral and/or bacterial respiratory infections are the most commonly associated triggers of COPD exacerbations. Respiratory viruses are detected in 20-60% of acute exacerbations of COPD [Kurai, 2013].

High efficiency lung delivery of broad spectrum CCI15106-containing engineered particles will establish an antiviral state in the lung. This has the potential to prevent the establishment or spread of the virus in the lower respiratory tract from the upper respiratory tract and/or increase the viral clearance translating to prevention of an exacerbation or a decrease in exacerbation severity and/or duration.

CCI15106 has been previously administered to humans in a different formulation, CCI15106: Trehalose: Trileucine 35/55/10 w/w 1 µm pollen shape PRINT particles (CCI15106 capsules for inhalation, referred to as CCI15106-CFI). Forty eight healthy participants have been administered a single dose of that formulation in one FTiH study 202031 and 12 participants received placebo. This study was planned as a double-blind (sponsor unblind), randomized, placebo-controlled, single and repeat escalating dose study to investigate the safety, tolerability, and pharmacokinetics of CCI15106-CFI in healthy participants and participants with moderate chronic obstructive pulmonary disease (COPD). In the single dose part of the study, CCI15106-CFI was administered by inhalation using Modified Air Inlet Rotahaler device at doses of 7.5 mg, 15 mg, 30 mg, and 60 mg. Overall, no clinically meaningful changes in vital signs or electrocardiograms (ECGs) were observed. There were no serious adverse events (SAEs) reported. Of the 60 subjects in the study, 25 reported adverse events (AEs) and 12 reported possibly drug-related AEs. The most common AEs were headache and cough (11 and 3 subjects, respectively). The comprehensive review conducted after single dose cohorts revealed acceptable safety profile, but lung epithelial lining fluid (ELF) levels of CCI15106 measured with 30 or 60 mg dose were below the levels predicted by preclinical evaluations and the increase in dose from 30 to 60 mg did not appear to result in a substantial increase in the lung concentration. Development of the CCI15106-CFI formulation was terminated before dosing repeat dose or COPD cohorts as a new formulation (CCI15106-IP) was developed that has higher ratio of active pharmaceutical ingredient to inactive ingredients per unit of powder and allows achieving the same dose in 1 capsule instead of 4. This is expected to lead to a higher lung ELF Cmax. The decision to terminate was not based on safety data.

Marketed formulations of CCI15106 are classified as teratogenic and is contra-indicated in women who are pregnant and in male partners of pregnant women. Currently approved aerosolised forms of CCI15106 are recommended to be administered in a negative pressure environment [Virazole USPI 2013]. It is important to understand whether bystanders may be exposed to CCI15106 when it is used by patients in a dry

2016N290366_02 **CONFIDENTIAL** 205822

powder, inhaled form. The most likely route of exposure of bystanders will be through inhalation of powder released during dosing. The study aims to replicate the real-life scenarios of dosing as close as possible. Real-life scenarios may include dosing of multiple patients in a single room in a nursing home or dosing of a single patient at home. A realistic worst-case scenario is dosing of multiple patients in a standard size room in a nursing home.

